## 13. PSYCHIATRIC HISTORY

Summary of psychiatric history information will be presented for the ISAF population. OSAF population will be used for the listing.

The number and percentage of subject's psychiatric history will be summarized by treatment (dose level of Lurasidone injectable suspension and pooled placebo) and overall.

Summary of psychiatric history will include number and percentage of schizophrenia subtype diagnosis, age at initial onset of schizophrenia, duration of schizophrenia from initial onset to

---

Document:

Author:

Version Number:  
Version Date:

Final Draft  
11APR2019

Template No: CS\_TP\_BS016 Revision 4  
Effective Date: 01Apr2016

Reference: CS\_WI\_BS005

screening (years), number of prior hospitalizations for schizophrenia, and proportion of subjects with other psychiatric disorders present.

Duration of schizophrenia (years) = (Date of informed consent - date of schizophrenia onset)/365.25

Age at onset of schizophrenia (years) = date of schizophrenia onset – date of birth)/365.25

For subjects with partial onset dates of schizophrenia, impute the onset date using the following rules:

- If only day unknown, impute as the earlier of: last day of the month, or date of ICF.
- If both month and day unknown, impute as the earlier of: 31st December of the year, or date of ICF.

Data listing of psychiatric history will also be provided.

## 14. PRIOR AND CONCOMITANT MEDICATIONS

Summary of medications will be presented by oral and injectable treatment groups in the safety population, and coded using ATC (Anatomical Therapeutic Chemical) classification (i.e. ATC level 3) and preferred drug name according to the World Health Organization Drug (WHODRUG) version 2018 March 01 or more recent. ATC Level 2 will be used if ATC Level 3 is not available. OSAF population will be used for the listing.

Prior and Concomitant Medications for the oral Lurasidone tablet period:

- Prior Medication are all medications with the start date or an end date prior to the first dose of oral Lurasidone tablet period.
- Concomitant Medication are all medications with a start date or an end date on or after the date of the first dose of oral Lurasidone tablet period.

Concomitant Medications for the double-blind injection period is defined as:

- All medications with a start or an end date that is on or after the Day 1 of the double-blind injection period as well as those that were marked as “ongoing” during that period.

Concomitant Medications for both the oral Lurasidone tablet period and the double-blind injection period:

- A medication which begins prior to or during the Oral Lurasidone tablet period and continues into the double-blind Injection period will be considered a concomitant medication in both

---

Document:

Author:

Version Number:  
Version Date:

Final Draft  
11APR2019

Template No: CS\_TP\_BS016 Revision 4  
Effective Date: 01Apr2016

Reference: CS\_WI\_BS005

periods. The same medication may be counted in both treatment periods for the same subject if it was taken during both periods.

The number and percentage of subjects using each prior medication will be summarized. Subjects with multiple uses of a medication will be counted only once for a given ATC class or preferred term.

The number and percentage of subjects using each concomitant medication will be summarized for the oral Lurasidone tablet period and for the double-blind injectable period by dose of Lurasidone injectable suspension and pooled placebo. Subjects with multiple uses of a medication will be counted only once for a given ATC class or preferred term.

Listing of prior and concomitant medications taken by subjects will also be provided.

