10.5.4.1. Day 29 (End of Safety and Tolerability Observation and Beginning of Restabilization)

- Awaken subject (if inpatient).
- Provide meals (if inpatient).
- Admit subject to clinic (if previously discharged).
- Perform Physical Examination.
- Record Weight and BMI.
- Obtain Vital Signs (approximately time matched to the injection predose timepoint on Day 1).
- Perform 12-Lead ECG (approximately time matched to the injection predose timepoint on Day 1).
- Collect Blood and Urine Samples for Clinical Laboratory Tests on (time matched to the injection predose timepoint on Day 1):
 - Hematology
 - Serum Chemistry
 - Urinalysis
 - Lipid Panel
 - Coagulation Panel
 - Thyroid Panel
- Obtain Blood Sample for Serum Prolactin.
- Obtain Blood Sample for PK.
- Obtain Blood Sample for b-hCG Serum Pregnancy Test (female subjects).
- Obtain Urine Sample for Urine Drug Screen and Urine Alcohol Test.
- Administer C-SSRS (Since Last Visit version).

- Administer PANSS.
- Subject Injection Site Pain Assessment.
- Investigator Injection Site Safety Assessment.
- Record Concomitant Medications.
- Reintroduce prior psychotropic medications.
- Record Adverse Events.

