## 18.3. ECG EVALUATIONS

Results from the central ECG (Electrocardiogram) Reading Centre will be included in the reporting of this study. Safety population will be used.

ISAF population will be used for all ECG summaries. OSAF population will be used for the listings.

The following ECG parameters will be reported for this study:

- PR Interval (msec)
- QRS Interval (msec)
- QTcF Interval (msec)
- QTcB Interval (msec)
- QT Interval (msec)
- HR (bpm)
- Overall assessment of ECG (Investigator's judgment):
  - Normal
  - Abnormal, Not Clinically Significant (ANCS)
  - Abnormal, Clinically Significant (ACS)

The following summaries and listings will be provided for ECG data:

- Observed values and changes from baseline will be presented at each evaluation timepoint and by treatment. Data will be summarized using descriptive statistics (n, mean, mean, median, minimum, maximum)

Summary of ECG categories of Markedly Abnormal Criteria will be summarized by timepoint and by

---

Document:

Author:

Version Number:  
Version Date:

Final Draft  
11APR2019

Template No: CS\_TP\_BS016 Revision 4  
Effective Date: 01Apr2016

Reference: CS\_WI\_BS005

treatment in frequency tables with counts and percentages for number of subjects. This will include overall for the oral period and double-blind injection period. The overall oral period includes Day -7, Day -6, Day 1 (Predose) and Baseline and all unscheduled visits within this period. The overall double-blind (DB) injection period includes Day 1 (postdose timepoints) to Day 61 and all unscheduled visits within this period.

- Listing of Electrocardiogram clinical interpretation of ECG findings including Markedly Abnormal Criteria

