### ALGORITHM FOR ADVERSE EVENTS:

#### ORAL LURASIDONE TABLET PERIOD

START DATE	STOP DATE	ACTION
Known	Known	If start date < oral tablet start date, then not AE If start date >= oral tablet start date and before injection start date, then AE
	Partial	If start date < oral tablet start date, then not AE If start date >= oral tablet start date, and before injection start date then AE
	Missing	If start date < oral tablet start date, then not AE If start date >= oral tablet start date and before injection start date, then AE
Partial, but known components show that it cannot be on or after oral tablet start date	Known	Pre-treatment events
	Partial	Pre-treatment events
	Missing	Pre-treatment events
Partial, could be on or after oral tablet start date and before injection start date,	Known	If stop date < oral tablet start date, then Pre-treatment events If stop date >= oral tablet start date and before injection start date, then AE
	Partial	Impute stop date as latest possible date (i.e. last day of month if day unknown or 31st December if day and month are unknown), then: If stop date < oral tablet start date, then Pre-treatment events If stop date >= oral tablet start date and before injection start date, then AE
	Missing	Assumed AE

Document:

Author:

Version Number:  
 Version Date:

Final Draft  
 11APR2019

Template No: CS\_TP\_BS016 Revision 4  
 Effective Date: 01Apr2016

Reference: CS\_WI\_BS005

START DATE	STOP DATE	ACTION
Missing	Known	If stop date < oral tablet start date, then Pre-treatment events If stop date >= oral tablet start date and before injection start date, then AE
	Partial	Impute stop date as latest possible date (i.e. last day of month if day unknown or 31st December if day and month are unknown), then: If stop date < oral tablet start date and before injection start date, then not AE If stop date >= oral tablet start date and before injection start date, then AE
	Missing	Assumed AE

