## ALGORITHM FOR PRIOR / CONCOMITANT:

### ORAL LURASIDONE TABLET PERIOD

START DATE	STOP DATE	ACTION
Known	Known	If stop date $<$ oral tablet start date, assign as prior  If both start date and stop date $\geq$ oral tablet start date, assign as concomitant  If stop date $\geq$ oral tablet start date and start date $<$ oral tablet start date, assign as both prior and concomitant
	Partial	Impute stop date as latest possible date (i.e. last day of month if day unknown or 31 st December if day and month are unknown), then:  If stop date $<$ oral tablet start date, assign as prior  If both start date and stop date $\geq$ oral tablet start date, assign as concomitant  If stop date $\geq$ oral tablet start date and start date $<$ oral tablet start date, assign as both prior and concomitant
	Missing	If stop date is missing then

Document:

Author:

Version Number:  
 Version Date:

Final Draft  
 11APR2019

Template No: CS\_TP\_BS016 Revision 4  
 Effective Date: 01Apr2016

Reference: CS\_WI\_BS005

START DATE	STOP DATE	ACTION
		
If start date <math>\geq</math> oral tablet start date, assign as concomitant
 
If start date <math><</math> oral tablet start date, assign as both prior and concomitant

Partial	Known	
Impute start date as earliest possible date (i.e. first day of month if day unknown or 1st January if day and month are unknown), then:
 
If stop date <math><</math> oral tablet start date, assign as prior
 
If both start date and stop date <math>\geq</math> oral tablet start date, assign as concomitant
 
If stop date <math>\geq</math> oral tablet start date and start date <math><</math> oral tablet start date, assign as both prior and concomitant

	Partial	
Impute start date as earliest possible date (i.e. first day of month if day unknown or 1st January if day and month are unknown)
 
Impute stop date as latest possible date (i.e. last day of month if day unknown or 31st December if day and month are unknown), then:
 
If stop date <math><</math> oral tablet start date, assign as prior
 
If both start date and stop date <math>\geq</math> oral tablet start date, assign as concomitant
 
If stop date <math>\geq</math> oral tablet start date and start date <math><</math> oral tablet start date, assign as both prior and concomitant

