	Missing	
Impute start date as earliest possible date (i.e. first day of month if day unknown or 1st January if day and month are unknown), then:
 
If start date <math>\geq</math> oral tablet start date, assign as concomitant

Document:

Author:

Version Number:  
 Version Date:

Final Draft  
 11APR2019

Template No: CS\_TP\_BS016 Revision 4  
 Effective Date: 01Apr2016

Reference: CS\_WI\_BS005

Statistical Analysis Plan

PROTOCOL D1052024  
 Page 55 of 66

START DATE	STOP DATE	ACTION
		If start date < oral tablet start date, assign as both prior and concomitant
Missing	Known	If stop date < oral tablet start date, assign as prior  If stop date >= oral tablet start date, assign as both prior and concomitant
	Partial	Impute stop date as latest possible date (i.e. last day of month if day unknown or 31 st December if day and month are unknown), then:  If stop date < oral tablet start date, assign as prior  If stop date >= oral tablet start date, assign as both prior and concomitant
	Missing	Assign as both prior and concomitant

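### SAP 14 and Appendix 2 set no end to oral-period concomitant medication, so every drug first taken after the injection is also counted in the Oral Lurasidone 80mg column of Table 14.1.5.2

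*SAP*

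**What the plan says.** SAP section 14 divides concomitant medication into an oral tablet period and a double-blind injection period and summarises each. Table 14.1.5.2 reports the result, and SAP Appendix 1 lists Oral Lurasidone 80mg as a treatment column.

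- **Oral period, section 14:** "all medications with a start date or an end date on or after the date of the first dose of oral Lurasidone tablet period".
- **Oral period, Appendix 2, both dates known:** "If both start date and stop date $\geq$ oral tablet start date, assign as concomitant".
- **Oral period, Appendix 2, start date missing:** "If stop date >= oral tablet start date, assign as both prior and concomitant".
- **Injection period, section 14:** "All medications with a start or an end date that is on or after the Day 1 of the double-blind injection period", plus drugs marked as ongoing.
- **Both periods, section 14:** a drug is concomitant in both if it began before or in the oral period and carried on into the injection period. The section adds: "The same medication may be counted in both treatment periods for the same subject if it was taken during both periods".

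Two other parts of the SAP do close the oral period. The oral-period AE algorithm in Appendix 2 has: "If start date >= oral tablet start date and before injection start date, then AE". SAP 18.3 on ECGs has: "The overall oral period includes Day -7, Day -6, Day 1 (Predose) and Baseline and all unscheduled visits within this period".

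Protocol 9.5.3 permits rescue drugs in the treatment and post-treatment periods. The Day 29 procedures in Protocol 10.5.4.1 include: "Reintroduce prior psychotropic medications". Protocol 14.3.5.8 classifies medications against a single dose date with no oral-period split, so it does not supply the missing limit.

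**The concern.** The oral-period rule has a lower limit and no upper limit. A drug first given on Day 10 meets it simply because Day 10 falls after Day -7. The rule therefore collects everything taken for the rest of the study, although the column is labelled as the tablet period.

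Table 14.1.5.2 is the only concomitant-medication summary listed in SAP Appendix 4. Each subject is counted once per ATC class or preferred term, so a reader of the table cannot separate use during the tablet challenge from later use. The oral column could show rescue drugs for movement symptoms or agitation that were first needed after the injection. It could also show antipsychotics in a stretch of the study that follows washout.

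**Working it through.** There is no planned figure to reproduce, because this is a classification rule. The check applies each rule to illustrative records.

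**Inputs.** First oral dose on Day -7 and injection on Day 1 (Protocol 6.1). SAP 7.1 has no Day 0. Follow-up is on Day 61 ± 2. Prior medication, including antipsychotics, restarts on Day 29 (Protocol 6.1 and 10.5.4.1). Protocol 9.5.1 instead bars these drugs until Day 30 is complete. Those passages need reconciling, but either date falls after the injection and gives the same result here.

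**Rules.**
- Section 14, oral: start ≥ -7 or stop ≥ -7.
- Appendix 2, oral, start known: stop ≥ -7 or stop missing. The drug is also prior if start < -7.
- Injection: stop ≥ 1 or ongoing.
- Oral period closed at injection: start < 1, and stop ≥ -7 or ongoing.

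If start ≥ 1 then start ≥ -7, so every drug first taken after the injection satisfies the oral rule. No dated row of the Appendix 2 oral table removes it.

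| Illustrative record | Sec. 14 oral | App. 2 oral | Injection | Oral if closed |
|---|---|---|---|---|
| Antipsychotic stopped Day -9 | no | prior only | no | no |
| Lorazepam Day -5 to -4 | yes | yes | no | yes |
| Benztropine Day -4 to 10 | yes | yes | yes | yes |
| Lorazepam Day 3 | yes | yes | yes | no |
| Benztropine Days 10 to 12 | yes | yes | yes | no |
| Antipsychotic from Day 29, ongoing | yes | yes | yes | no |
| Analgesic Days 45 to 46 | yes | yes | yes | no |

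All 4 of the 4 records that start after the injection are oral-period concomitant as written. With the period closed, 0 of 4 are, and all four stay in the injection column. The oral-only record and the spanning record keep their correct places.

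**A side result.** A long-standing drug that began on Day -300 and is ongoing fails the section 14 oral bullet, which does not mention ongoing use, but is prior and concomitant under Appendix 2. The closed rule classes it correctly.

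**Window.** As written: Day -7 to Day -1 is 7 days and Day 1 to Day 61 is 61 days, so 7 + 61 = 68 days. Intended: 7 days. Ratio: 68/7 = 9.7.

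**The case against.** The strongest reply is that section 14 already shows its intent. It describes a both-period drug as one begun before or in the oral period and continued past the injection, and benztropine started on Day 10 does not fit. A programmer could follow that sentence. This stands as evidence of intent, but it sets no end date, and the algorithm to be programmed contradicts it. The SAP is inconsistent with itself, and the operative rule gives the unintended answer.

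The reply is also right about consequence. Post-injection drugs still enter the injection columns, so each dose group and pooled placebo stays complete. Medication use is not an endpoint, and SAP 18 plans no statistical comparison of safety data unless otherwise specified.

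A reader might infer more than the documents support:

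- *That rescue use is moved from the injection to the tablets.* It is duplicated, not moved.
- *That the SAP allows counting in both periods only for drugs taken in both.* The SAP says such a drug may be counted twice. It does not say that no other drug may be.
- *That the table is the check on an antipsychotic-free run-in.* The SAP gives it no such role. SAP 10 reviews disallowed drugs likely to affect PK as important deviations, and Listing 16.2.4.4 covers prior and concomitant medications.
- *That 57% (40/70) to 100% (40/40) of the oral column would be psychotropic users against a true 0%.* This assumes that all 40 injected subjects reach Day 29 and restart a psychotropic. It also treats 70, the overall planned number, as a possible count of orally dosed subjects. It compares psychotropics with antipsychotics, and the table has no pooled psychotropic row. The 0% is not secure either, because partial stop dates are imputed to the latest possible date and Protocol 9.5.1 makes discontinuation subject to tolerability.

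**Conclusion.** The oral-period rule is wrong as written. Section 14 and every dated row of the Appendix 2 oral-period medication table class any drug first taken on or after Day 1 as oral-period concomitant. That conflicts with section 14's description of both-period drugs and with the oral-period end used for AEs and ECGs. Nothing else in the documents supplies the limit.

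The effect is confined to the Oral Lurasidone 80mg column of Table 14.1.5.2, whose window is about 68 days instead of 7. The injection-dose and placebo columns, the AE, PK and PANSS outputs and the dated listing are unaffected.

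The share of subjects wrongly counted cannot be derived from the documents. It would be large if most injected subjects reach Day 29, restart prior drugs and have the restart recorded as a new dated entry. The conclusion assumes that the rules are programmed as they stand.

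**What to change.** In SAP 14 and each oral-period row of the Appendix 2 medication algorithm, class a drug as oral-period concomitant only if both conditions hold:

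1. its start date, known or imputed to the earliest possible date, is before the injection date; and
2. its stop date is on or after the first oral dose, or it is ongoing.

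Two conventions must be stated with it:

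- **Missing start date.** No start date is imputed in these rows, so condition 1 cannot be applied. One option is to keep the conservative assignment to both periods and footnote it. The footnote should also say that a partial start date imputed to its earliest possible date can still place a post-injection drug in the oral column.
- **Subjects never injected.** They have no injection date. Name an end to their oral period, such as reintroduction of prior medication (which Protocol 6.2.1 requires before unused alternates are discharged) or end of study/early termination.

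The cost is one added condition and two conventions in the SAP text, the matching change in the derivation program, and a table footnote. No new data are needed.

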## **15. STUDY DRUG EXPOSURE**

Because this is a single dose study, study drug exposure will not be summarized as each randomized subject must have the same exposure.

## **16. STUDY DRUG COMPLIANCE**

Because this is a single dose study, treatment compliance will not be summarized as each randomized subject must have the same compliance.

A data listing, by subject, containing the study drug dosing will be provided.

## **17. PHARMACOKINETIC ANALYSES**

Blood samples for serum PK assessment will be collected at predose and 2 hours after tablet administration, and at predose and multiple timepoints up to 1440 ( $\pm 48$ ) hours after the injection dose. Urine samples for PK assessment will be collected at predose and up to 144 hours after the injection dose.

Analysis of the PK of lurasidone and metabolites (ID-14283, ID-14326, ID-11614, ID-20219 and ID-20220) in serum and urine will be the responsibility of the clinical pharmacokineticist at IQVIA. The PK summaries, data listings, figures, and the statistical analysis of the PK parameter and concentration data will be the responsibility of the biostatistician at IQVIA.

Subjects will be analyzed according to analyte and treatment received using actual time the sample

---

Document:

Author:

Version Number:  
Version Date:

Final Draft  
11APR2019

Template No: CS\_TP\_BS016 Revision 4  
Effective Date: 01Apr2016

Reference: CS\_WI\_BS005

was collected. For SRT analyses, nominal times will be used for timing of the samples collected.

Pharmacokinetic variables (serum concentrations, urine amounts, and serum and urine PK parameters) will be summarized using descriptive statistics, including population size (N for sample size and n for available data), mean, SD, CV%, median, minimum, and maximum. For serum PK parameters, geometric mean (Geo mean), and GCV% will also be included, except for  $t_{max}$ , where only n, median, minimum, and maximum will be provided.

Source data (e.g., serum and urine concentrations) will be reported and analyzed to the same precision that it is received, regardless of how many significant figures or decimals the data carry. Derived data (e.g., urine amounts and parameters, serum PK parameters) will be rounded for reporting purposes both in the summary tables and by-subject listings. For the calculation of descriptive statistics and the statistical analysis, rounded values as presented in the data listings will be used. For most derived PK parameters, 3 significant digits will be used as the standard rounding procedure, with the following exceptions:

- Parameters directly derived from source data (e.g.,  $C_{max}$ ) will be reported and analyzed with the same precision as the source data.
- Parameters derived from actual elapsed sample collection times (e.g.,  $t_{max}$ ) will be reported in hours with 2 decimal places.
- Apparent terminal rate constant ( $\lambda_z$ ) will be reported with 4 decimal places.

Reporting of mean (arithmetic and geometric), SD, minimum, median, and maximum will follow the rounding convention of the individual PK data and, in inferential analysis tables, associated CIs will be reported as percentages (%) to 2 decimal places. Coefficient of variation will always be reported to 1 decimal place.

Extra measurements (such as unscheduled or repeat assessments) will not be included in the descriptive statistics but will be included in subject listings. Pharmacokinetic summaries and inferential analyses (dose proportionality assessment) will be conducted for all subjects in the PK population. Data from subjects excluded from an analysis population will be included in the data listings, but not in the summaries or inferential analyses.

In general, serum (concentrations and parameters) and urine (amounts, fractions excreted, and parameters) PK data will be presented by analyte, dose level and subdivided by gender, as appropriate. Some minor modifications to the planned design of tables, figures, and listings may be necessary to accommodate data collected during the actual study conduct.

In the case of an important protocol deviation or event (see Section 10), affected PK data collected will be excluded from the summaries and statistical analyses, but will still be reported in the study

---

Document:

Author:

Version Number:  
Version Date:

Final Draft  
11APR2019

Template No: CS\_TP\_BS016 Revision 4  
Effective Date: 01Apr2016

Reference: CS\_WI\_BS005

result listings.

